9.8 Investigator Training

The participating investigator will be trained in the use of the FARAPULSE Endocardial Multi Ablation System prior to participating in the study. Device training will be conducted by the Sponsor or its representatives. All device training will be documented in a training log that will be maintained in the Regulatory Site Binder.

9.9 Site Training

To ensure accurate, complete and reliable data, the Sponsor or its representatives will provide instructional material to the site, as appropriate; instruct the

investigator and study personnel on the CIP, the completion of the CRFs including CRF Instructions, and study procedures; communicate regularly with site personnel via mail, email, telephone, and/or fax; and make periodic monitoring visits to the site. During those visits, the Sponsor or its representatives will monitor the subject data recorded in the CRFs against the source documents at the site for all enrolled subjects.

9.10 Clinical Events and Data Monitoring Committee

The Sponsor has established an external group of expert physicians who are not investigators to serve as the Clinical Events and Data Monitoring Committee (CEDMC). This group will consist of a panel of 3 experienced, independent physicians who are not investigators and who will be supported by the Medical Monitor and Study Statistician. A combined CEDMC procedure is an appropriate structure for a 40 subject feasibility study.

The CEDMC will review and approve a Charter. The CEDMC will convene during the study to screen, classify and adjudicate all adverse events reported in the subject investigation as well as major study outcomes. The CEDMC will be provided with case summaries, relevant source documents and any other information required to evaluate and adjudicate the adverse events and study outcomes.

The CEDMC will also convene to review safety data and trends during the conduct of the study. This formal assessment will occur at a minimum after the enrollment of 20 and then 40 subjects. The CEDMC will recommend to the Sponsor whether a study pause or termination is required if it identifies a trend that indicates a danger to patient safety.

9.11 Data Management

Data management procedures will be included in the Study Management Plan.

CRFs will be made available to the participating site. Investigators are responsible for the accurate completion of patient CRFs during the study. The Investigator will ensure that complete, accurate and timely data on CRFs are completed, that protocol requirements are followed and that complications, adverse events and adverse device effects are correctly reported and investigated, as appropriate. The Investigator is expected to maintain all source documents as required by the CIP, including laboratory results, supporting medical records, and signed ICFs. The source documents will be used during the regular monitoring visits to verify information from the database against data contained on the completed CRFs.

After CRF Monitoring has been complete and deficiencies / discrepancies resolved, CRFs will be provided to the Sponsor or CRO, and data from the study will be entered from the CRFs into a central database. CRF data will be reviewed to identify any inconsistent or missing data and any adverse events. Any data issues are to be promptly addressed with the Investigator by the CRO.

9.12 Study Suspension or Early Termination

The study can be discontinued at any site at the discretion of the Investigator or study Sponsor for reasons including, but not limited to, the following:

- Occurrence of adverse events unknown to date in respect to their nature, severity, or duration, or the unexpected incidence of known adverse events.
- Obtaining new scientific knowledge that shows that the study is no longer valid or necessary.
- Data demonstrates a benefit to subjects who undergo percutaneous ablation with the FARAPULSE Endocardial Multi Ablation System making treatment without the FARAPULSE Endocardial Multi Ablation System unethical.
- Insufficient recruitment of subjects.
- Unanticipated adverse device effect (UADE) presenting an unreasonable risk to subjects (Sponsor may terminate the study immediately)
- Persistent non-compliance with the Clinical Investigation Plan.
- Persistent non-compliance with regulatory requirements.

If the study is discontinued or suspended prematurely, the Sponsor shall promptly inform the clinical investigator/ investigational center of the termination or suspension and the reason(s) for discontinuation / suspension. The national and local regulatory authorities shall also be informed promptly and provided with the reason(s) for the termination or suspension by the Sponsor, CRO or by the clinical investigator/ investigation center. Further, if the study is discontinued or suspended prematurely, patients enrolled to that point will continue to be followed for safety through the 12-month timepoint.

9.13 Criteria for Suspending/ Terminating a Study Center

Sponsor reserves the right to stop the screening of subjects at the study center at any time after the study initiation visit if no subjects have been enrolled or if the center has multiple or severe protocol violations without justification or fails to follow remedial actions.

Possible reasons for suspending/ terminating the study center include, but are not limited to:

- Repeated failure to complete CRFs prior to scheduled monitoring visits;
- Failure to obtain written informed consent using the EC-approved ICF;
- Failure to report SAEs/ USADEs to Sponsor within 24 hours of knowledge;
- Loss of (or unaccounted for) investigational product inventory or repeated failure of device accountability.

9.14 Deviations from the Clinical Investigation Plan

The Investigator is not allowed to deviate from the approved CIP except in emergency circumstances.

The Investigator must notify the Sponsor and the CRO of any deviation from the CIP and document the reason for the deviation.

The Investigator shall notify the Sponsor and the reviewing EC of any deviation from the CIP, as per national requirements, to protect the life or physical well-being of a subject in an emergency. Such notice shall be given as soon as possible, but in no event later than five (5) working days after the emergency occurred.

10. Regulatory Considerations

10.1 Maintaining Records

The Sponsor and CRO will maintain copies of critical correspondence, regulatory approvals, Trial Master Files, clinical data, shipment of devices, adverse events, serious adverse events, serious adverse device effects and other records related to the clinical study.

Trial records will be maintained for a minimum of 3 years following the completion of research activities and closure of the study with Ethics Committees, whichever is longer.

10.2 Data Handling and Record Keeping

10.2.1 Source Documents

The Investigator must maintain detailed source documents on all subjects who are enrolled or who undergo screening in the study. Source documents include but are not limited to, subject medical records, hospital charts, clinic charts, investigator subject study files, as well as the results of diagnostic tests (e.g., laboratory tests, hemodynamic studies).

The following minimum information should be entered into the subject's medical record:

- The date the subject entered the study and the subject number.
- The Clinical Investigation Plan number and the name of the Sponsor.
- The date that Informed Consent was obtained and signed by the patient and Investigator.
- Evidence that the subject meets the study eligibility requirements (e.g., medical history, study procedures and/or evaluations).
- The dates of all study related subject visits.
- Evidence that required procedures and/or evaluations were completed.
- Use of any concurrent medications.
- Documentation of specific device used.
- Occurrence and status of any adverse events (AEs / SAEs)
- The date the subject exited the study and a notation as to whether the subject completed the study or was discontinued, including the reason for discontinuation.

10.2.2 Data Collection

The Investigator must maintain detailed records on all subjects who sign the ICF and begin the pre-procedure evaluation. Data for enrolled subjects is transcribed onto CRFs provided by the Sponsor or designee. All data should be transcribed completely, promptly and legibly. Corrections should be made in a manner that does not obscure or eliminate the original error, by striking through the original data with one line, and initialing and dating the change, along with the reason for the change (if not obvious). Original CRF pages will be collected by the Sponsor

or Sponsor's designee after they are reviewed by the study monitor. The investigator should maintain a copy of all completed CRFs from this study.

Study exit forms will be completed for all enrolled subjects, regardless if they did or did not complete the study (e.g., subject discontinuation, study termination). The Sponsor and investigational site will maintain all records pertaining to this study in accordance with local and national regulations. Prior to the destruction of study records the Investigator or his representative shall contact the Sponsor to ensure that they no longer need to be retained. In addition, Sponsor shall be contacted if the Investigator plans to leave the investigational site so that arrangements can be made for the handling or transfer of study records.

10.3 Ethics Committee and Competent Authority Approval

Regulatory approvals must be obtained prior to enrollment of the first patient. The Sponsor is responsible for obtaining regulatory and local approvals for the study. The Sponsor or its designated representative will require a copy of any IC and CA correspondence, as well as the final approval letter from the EC and CA, where applicable.

An Investigator may not make CIP changes without prior approval by the Sponsor. All significant CIP changes that may affect the following must be submitted and approved by the EC and CA before initiating the change:

- Validity of the data or information resulting from the completion of the approved CIP
- Relationship of the likely subject risk to benefit relied upon to approve the CIP
- Scientific soundness of the CIP
- Rights, safety, or welfare of the human subjects involved in the investigation

The Sponsor will notify the investigational site of such changes to ensure the study continues to be conducted consistent with the approved CIP.

10.4 Procedure for Amending the CIP

The process of amending the CIP and/or related documents is the responsibility of the sponsor. The procedure for amending the CIP shall be as follows:

- The Sponsor, Investigator, or other relevant party (e.g. EC, CA, CEDMC) may recommend modification of the CIP.
- The Sponsor will then modify as necessary the CIP and any associated documents requiring amendment as a result of the modification(s).
- The Sponsor or designated CRO will then submit the revised CIP and any other affected documents to the EC and CA for approval, per regulation.
- Once all required approvals are obtained, the site will be trained to the latest approved version of the CIP and any other affected documents.

DocUUID : f0edee1a-3b43-454d-8bb3-52919e5ba253

	STATISTICAL ANALYSIS PLAN	FARAPULSE PersAFOne SAP V1.0 PERSAFONE Page 11 /49
---	----------------------------------	--

1. OVERVIEW

This statistical analysis plan (SAP) describes the planned statistical analyses of the data collected during the clinical study PersAFOne.

This SAP provides additional details concerning the statistical analyses outlined in the protocol (1309_CS0607_PersAFOne Clinical Investigation Plan_Rev C_08Oct2019 dated 08Oct2019).

1.1. Study Objective

The objective of this safety and feasibility study is to assess whether the endocardial creation of electrically nonconductive lesions via PEF catheter ablation applied using the FARAPULSE Endocardial Multi Ablation System is a feasible and safe treatment for Persistent AF and associated AFL.

1.2. Study Design

This study is a prospective, multi-center, unblinded single arm safety and feasibility study.

Subjects will undergo percutaneous PEF ablation for pulmonary vein isolation and at the clinical discretion of the investigator receive PEF ablation of additional arrhythmogenic locations. Subjects will be followed at 30 days, 75 days, 6 months and 12 months for adverse events, recurrence of arrhythmia after a 90-day Blanking Period and other relevant outcome measures.

1.3. Study Plan

1.3.1. Patient's Follow-up

7 visits are scheduled:

- Visit 1: Baseline
- Visit 2: Index procedure
- Visit 3: Pre-Discharge
- Visit 4: 30-day Visit
- Visit 5: 75-day Visit and Remapping Procedure
- Visit 6: 6 Months Visit
- Visit 7: 12 Months Visit

1.3.2. Study Device use

The FARAPULSE Endocardial Multi Ablation System is comprised of the following devices:

- FARAWAVE Endocardial Ablation Catheter
- FARAFLEX Endocardial Ablation Catheter
- FARASTAR Endocardial Generator System
- FARADRIVE Deflectable Sheath.

The FARAPULSE Endocardial Multi Ablation System is indicated for the treatment of drug refractory, recurrent, symptomatic persistent atrial fibrillation.

CONFIDENTIEL / CONFIDENTIAL

Toute reproduction ou distribution, totale ou partielle, de ce document, sans autorisation préalable de ICON PLC est interdite.
Reproduction and distribution of this document, in whole or in part, is strictly forbidden without prior authorization from ICON PLC.

	STATISTICAL ANALYSIS PLAN	FARAPULSE PersAFOne SAP V1.0 PERSAFONE Page 12 /49
---	----------------------------------	--

The FARAFLEX Endocardial Ablation Catheter is used as an adjunctive device in the endocardial treatment of persistent atrial fibrillation with the following intended uses:

- Gap ablation to complete electrical isolation of the pulmonary veins,
- Focal ablation of cardiac arrhythmias, and
- Creation of ablation line between the inferior vena cava and the tricuspid valve.

1.3.3. Study Assessments

The following flowchart applies to the study:

Assessment	Baseline	Procedure	Pre-Discharge	30-Days Post-Procedure (± 7 days)	75-Days (± 15 days)	6-Month (180 ± 30 days)	12-Month (365 ± 30 days)	Unscheduled
Medical History, CHA ₂ DS ₂ -VASc	X							
AFD and Anticoagulant Medications	X		X	X	X	X	X	X
Symptoms of recurrent arrhythmia				X	X	X	X	X
History of cardioversions, ablations, hospital admissions since last visit			X	X	X	X	X	X
Pregnancy test (for females of childbearing potential)	X	X			X			
12-lead ECG	X		X	X	X	X	X	X
24-Hour Continuous ECG Monitor (e.g., Holter)						X	X	
Cardiac CT/MRI for LA and PV dimensions	X				X			
Mediastinal MRI			X ¹					
TEE or other imaging modality (to exclude left atrial thrombus)	X							
Electroanatomical Mapping		X			X			
Event Monitor readiness/compliance					X	X	X	X
NIHSS	X		X					
Neurologic exam			X ²					
NYHA Classification	X		X	X	X	X	X	X
Fluoroscopic Examination of Diaphragm		X			X if remapped, X ³ if not	X ³	X ³	
Adverse Events		X	X	X	X	X	X	X

¹ At investigator's discretion

² If NIHSS score has increased by 2 or more points or if clinical suspicion of stroke/TIA

³ If the Index Procedure or Remap Procedure study indicated decreased phrenic nerve function and resolution has not yet been demonstrated.

2. STATISTICAL METHODS

2.1. General Statistical Considerations

2.1.1. Time Points Definition

Baseline data is defined as the last available observation recorded before the first study device exposition for the patient.

Visit(n) data is defined as the last available observation on or before the Visit(n) time point following the first study device exposition for the patient.

2.1.2. Handling Missing Data

In order to provide unbiased and informative findings, no replacement of missing values is planned for any parameters. Analyses is performed with all available data only.

Data collected by the Investigators and reviewed by the Clinical Event Committee (CEC):

CONFIDENTIEL / CONFIDENTIAL

Toute reproduction ou distribution, totale ou partielle, de ce document, sans autorisation préalable de ICON PLC est interdite.
Reproduction and distribution of this document, in whole or in part, is strictly forbidden without prior authorization from ICON PLC.

	STATISTICAL ANALYSIS PLAN	FARAPULSE PersAFOne SAP V1.0 PERSAFONE Page 13 /49
---	----------------------------------	--

When the data are collected by the investigators and reviewed by the CEC, the analysis will be as follows:

- The data reviewed by the CEC will prevail and will be analysed with no replacement of missing data from the CEC with the data collected by the investigator

2.1.3. Descriptive Statistics in Summary Tables

- *Continuous variables* will be summarized using standard quantitative statistics: number of non-missing observations, mean, standard deviation, median, quartiles and range (minimum and maximum observed values). The number of missing observations will also be specified.
- *Categorical variables* will be summarized using classical frequency statistics: number of non-missing observations and percentages by categories. Percentages will be calculated on the number of non-missing observations and will be displayed using one decimal. The number of missing observations will also be specified.

2.1.4. Inferential Analysis

- Confidence intervals:

When applicable, bilateral asymptotic or exact confidence intervals for binomial distributions will be calculated at the 95% level.

For categorical variables, if pertinent, the 95% asymptotic confidence interval will be calculated if theoretical assumptions are verified. If this is not the case, and the corresponding proportion is 0% or 100%, then the Agresti-Coull confidence interval will be calculated instead. In all other cases, the exact confidence interval will be calculated.

- Survival analysis:

Time-to-event variables will be described over time by survival curves as per the Kaplan-Meier method together with the associated estimators, considering the upper window of the corresponding visits. The survival rate will be presented at each time point (30 days, 90 days, 180 days, 365 days) and overall.

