1.3 Summary of FARAPULSE Clinical Studies

1.3.1 Endocardial Ablation Studies – The IMPULSE Study

FARAPULSE, Inc. initiated a safety and feasibility study at Na Homolce Hospital in Prague, Czech Republic and Hopital Cardiologique du Haut-Leveque in Pessac, France under the “IMPULSE” Protocol, CS0188. This study is being conducted using the FARAPULSE Endocardial Ablation System. Forty (40) patients were enrolled between January and December of 2018. Thirty (30) patients were enrolled in Prague and ten (10) were enrolled in Bordeaux. All patients were discharged in good condition. One patient was treated for tamponade at the conclusion of the Index Procedure and the event was resolved. Three patients were re-hospitalized for atrial arrhythmia and all of these events were resolved. One patient experienced a prolonged index hospitalization due to an arteriovenous groin fistula which was resolved. At the conclusion of the index Procedure, all (100%) pulmonary veins (PVs) were isolated using the FARAPULSE Endocardial Ablation System. Thirty-five (35) patients have returned for the protocol-defined 3-month remapping procedure to assess durable PV isolation. In these patients, 70% of PVs remained isolated. All PVs in fourteen (14) patients remained isolated. These results support the safety and performance of the system.

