2.4.4. Remapping at 75 Days

Descriptive statistical data will be used to draw up a recapitulation of the follow-up details at 75-day Visit and Remapping Procedure.

The following data will be presented on the ITT population:

Days follow up at remap, Durable PVI, LSPV chronic isolation, LIPV chronic isolation, LCPV chronic isolation, RSPV chronic isolation, RIPV chronic isolation, RMPV chronic isolation, CTI chronic isolation, LAPW chronic isolation, Number of veins durably isolated, Number of veins with gaps.

2.4.5. 6 and 12 Months follow up

Descriptive statistical data will be used to draw up a recapitulation of the follow-up details at 6 and 12 Months follow up.

The following data will be presented on the ITT population:

TTM compliance, Holter compliance (6 month and 12 month), Freedom from AF/AFL/AT (for patient On AADs and on patient Off AADs), Freedom from AF (for patient On AADs and on patient Off AADs), Freedom from AF/AFL/AT, no DCCV>90 days, no RF, no ablation >90 days (for patient On AADs and on patient Off AADs), Freedom from AF, no DCCV>90 days, no RF, no ablation >90 days (for patient On AADs and on patient Off AADs).

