4.1.4. Table 4. Procedure

	ITT Population	
	N = XX	
	Mean±S.D.	[95% CI]
Procedure time (hours)	Mean±S.D. Median (min, max) (Q1, Q3)	[95% CI]
Farawave dwell time (hours)	XX±X XX (XX, XX) (XX, XX)	[XX - XX]
PVI ablation time (hours)	XX±X XX (XX, XX) (XX, XX)	[XX - XX]

CONFIDENTIEL / CONFIDENTIAL

Toute reproduction ou distribution, totale ou partielle, de ce document, sans autorisation préalable de ICON PLC est interdite.
Reproduction and distribution of this document, in whole or in part, is strictly forbidden without prior authorization from ICON PLC.

ICON	STATISTICAL ANALYSIS PLAN	FARAPULSE PersAFOne SAP V1.0 PERSAFONE Page 36 /49
-------------	----------------------------------	--

	(XX, XX)	
CTI (FARAFLEX) dwell time (hours)	XX±X XX (XX, XX) (XX, XX)	[XX - XX]
LAPW ablation time (hours)	XX±X XX (XX, XX) (XX, XX)	[XX - XX]
Fluoroscopy time (min)	XX±X XX (XX, XX) (XX, XX)	[XX - XX]
Contrast volume (cc)	XX±X XX (XX, XX) (XX, XX)	[XX - XX]
IV fluid volume (cc)	XX±X XX (XX, XX) (XX, XX)	[XX - XX]
Total number of PVI applications	XX	NA
Number of applications/patient	XX±X XX (XX, XX) (XX, XX)	[XX - XX]
Number of applications/vein	XX	NA

CONFIDENTIEL / CONFIDENTIAL

Toute reproduction ou distribution, totale ou partielle, de ce document, sans autorisation préalable de ICON PLC est interdite.
Reproduction and distribution of this document, in whole or in part, is strictly forbidden without prior authorization from ICON PLC.

ICON	STATISTICAL ANALYSIS PLAN	FARAPULSE PersAFOne SAP V1.0 PERSAFONE Page 37 /49
-------------	----------------------------------	--

Number of LAPW applications	XX	NA
	N, n, n/N (%)	95% CI
Total number of veins treated	XX	NA
Total number of veins isolated	XX	NA
Of the total number of veins treated, the number of veins isolated	XX/XX (XX.X%)	[XX% - XX%]
CTI acute isolation	XX/XX (XX.X%)	[XX% - XX%]
Total number of CTI applications	XX	NA

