4.1.6. Table 6. Per Remapped Veins Analysis

	Veins Remapped N = XX	
	n/N (%)	[95% CI]
Number of veins durably isolated	XX/XX (XX.X%)	[XX% - XX%]
Number of veins with gaps	XX/XX (XX.X%)	[XX% - XX%]
Missing Data	XX	NA

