4.1.11. Table 11. Additional Endpoints

ITT Population		
N = XX		
	Mean±S.D.	
	Median (min, max) (Q1, Q3)	[95% CI]
Time to Therapeutic Failure (days)	XX±X XX (XX, XX) (XX, XX)	[XX - XX]
	n/N (%)	[95% CI]
Proportion of subjects with Early recurrence of atrial fibrillation (ERAF) by 90 days after the index procedure	XX/XX (XX.X%)	[XX% - XX%]
Proportion of all ablated pulmonary veins that are isolated at the Index Procedure using the study device	XX/XX (XX.X%)	[XX% - XX%]
Proportion of all ablated pulmonary veins isolated using the study device during the Index Procedure that remain isolated at the 75-day remapping procedure	XX/XX (XX.X%)	[XX% - XX%]

CONFIDENTIEL / CONFIDENTIAL

Toute reproduction ou distribution, totale ou partielle, de ce document, sans autorisation préalable de ICON PLC est interdite.
Reproduction and distribution of this document, in whole or in part, is strictly forbidden without prior authorization from ICON PLC.

	STATISTICAL ANALYSIS PLAN	FARAPULSE PersAFOne SAP V1.0 PERSAFONE Page 42 /49
---	----------------------------------	--

The proportion of attempted subjects that achieve Chronic CTI Success, defined as persistent bi-directional electrical block across the CTI assessed at the 75-day Remapping Procedure	XX/XX (XX.X%)	[XX% - XX%]
The proportion of attempted subjects that achieve Chronic Focal Success, defined as persistent electrical nonconductivity of all extra-PV tissue targeted for ablation in the Index Procedure, excluding the CTI	XX/XX (XX.X%)	[XX% - XX%]

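### SAP Tables 4, 6 and 11 put ordinary binomial 95% intervals on pooled veins; these are too narrow if the veins of one patient tend to succeed or fail together

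*SAP*

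**What the plan says.** SAP 2.1.4 is the only place in the SAP that sets interval methods for proportions, and protocol 5.1 gives the same general rule: "bilateral asymptotic or exact confidence intervals for binomial distributions will be calculated at the 95% level". The SAP then sets an order. The asymptotic interval is used if its assumptions are met. If they are not and "the corresponding proportion is 0% or 100%, then the Agresti-Coull confidence interval will be calculated instead". Finally, "In all other cases, the exact confidence interval will be calculated".

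Five table rows with a 95% CI column have the vein as their unit:
- Table 4: "Of the total number of veins treated, the number of veins isolated".
- Table 6, whose N is the count of veins remapped: "Number of veins durably isolated", and the matching row for veins with gaps.
- Table 11: "Proportion of all ablated pulmonary veins that are isolated at the Index Procedure using the study device", and the row for isolated veins that are still isolated at the remap.

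SAP 2.5 builds these numerators and denominators by adding up vein positions. SAP 2.4.4 names six of them ("LSPV chronic isolation, LIPV chronic isolation, LCPV chronic isolation, RSPV chronic isolation, RIPV chronic isolation, RMPV chronic isolation"), but neither document gives the average number of veins per patient. Neither mentions clustering, robust variance, a design effect or resampling by patient.

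Two earlier studies are summarised at both levels. For IMPULSE, with 35 patients remapped, protocol 1.3.1 says: "In these patients, 70% of PVs remained isolated. All PVs in fourteen (14) patients remained isolated". For PEFCAT, protocol 1.3.2 reports 49 patients remapped, 96% of veins isolated, and all veins isolated in 39 patients.

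**The concern.** The veins of one patient are treated by the same operator in the same session and the same atrium, so their outcomes may be alike. A binomial interval on pooled veins counts each vein as separate information. With positive correlation the effective number of observations is smaller than the vein count, and the printed interval is too short. The SAP's condition on theoretical assumptions does not repair this, since the exact and Agresti-Coull fallbacks also need independent units.

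What is at stake is the stated precision of acute isolation and 75-day durability per vein. The point estimates are not affected.

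**Working it through.** The table shells are empty and the documents state no vein-level interval, so there is no planned figure to reproduce. The check asks what the earlier studies say about correlation, and what that would do to the interval.

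**Inputs.** IMPULSE and PEFCAT figures are from protocol 1.3.1 and 1.3.2. The planned number is up to 40 patients (protocol 3.7); the Table 5 shell in the SAP shows N = 25. Veins per patient: m = 4, an assumption.

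**Step 1, IMPULSE.** With independent veins, the share of patients with all four isolated would be 0.70^4 = 24.0%, or 0.240 × 35 = 8.4 patients. Reported: 14/35 = 40%. The exact probability of 14 or more is 0.026 one-sided, about 0.052 doubled. Matching a beta-binomial with mean 0.70 to 40% gives a correlation of 0.29 (0.28–0.31 over rounding of the 70%). Sampling error is far larger than rounding error. The exact 95% interval for 14/35 is 23.9–57.9%, which just includes 24.0%. With the 70% held fixed, that corresponds to correlations from 0 to about 0.70. With m = 5 the point value is about 0.38.

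**Step 2, PEFCAT.** Independence predicts 0.96^4 = 84.9%, or 41.6 of 49 patients; 39 (79.6%) were reported, which gives no sign of positive correlation. However, 10 patients had at least one gap, and a figure that rounds to 96% allows at most 4.5% of veins with gaps. That needs at least 10/0.045 = 222.2, so 223 veins, or 223/49 = about 4.6 per patient. The figures do not fit m = 4. With m = 5 independence predicts 40.0 patients, again with no positive correlation.

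**Step 3, widening.** Design effect DE = 1 + (m − 1) × correlation; the width grows by √DE.

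| Correlation | DE | Width factor |
|---|---|---|
| 0.1 | 1.3 | 1.14 |
| 0.2 | 1.6 | 1.26 |
| 0.3 | 1.9 | 1.38 |
| 0.5 | 2.5 | 1.58 |

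**Step 4, examples at 90% isolated and correlation 0.3**, using effective n = veins/1.9:
- 25 patients, 100 veins: exact 82.4–95.1% becomes 78.6–96.6%.
- 40 patients, 160 veins: exact 84.3–94.2% becomes 81.5–95.5%; asymptotic 85.4–94.6% becomes 83.6–96.4%.

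**Step 5, coverage** of nominal 95% intervals, simulated from a beta-binomial with 25 patients, 4 veins and correlation 0.3, at true rates of 70, 85, 90 and 95%:
- Exact: about 87, 87, 85 and 92%.
- Asymptotic: about 84, 82, 82 and 76%. Part of the shortfall at 95% is the asymptotic interval's own weakness near the boundary, not clustering.

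With 40 patients and a true rate of 90%, the exact interval covers about 87%. At correlation 0.1 with 25 patients it covers about 92–96%, close to nominal.

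**Step 6, all veins isolated.** Agresti-Coull lower limits are 95.6% on 100/100 veins and 84.2% on 25/25 patients. The second equals a design effect of 4, which is complete correlation. At DE 1.9, effective n = 52.6. The adjusted n is 52.6 + 3.84 = 56.5, the adjusted proportion is (52.6 + 1.92)/56.5 = 0.966, and the lower limit is 0.966 − 1.96 × √(0.966 × 0.034/56.5) = about 91.9%.

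**The case against.** The study is descriptive. Protocol 5.3 and SAP 2.2 rule out formal hypothesis testing, and no success threshold hangs on these rows. Vein-level proportions are additional or procedural assessments. Acute procedural success and chronic procedural success are counted per subject, and each single-position row of Table 5 has one observation per patient, so the reader also gets results that clustering does not touch. All of this stands and limits the severity.

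The evidence for correlation is also thin. A reader might infer from IMPULSE that clustering is demonstrated and that 1.9 is the design effect to use. The documents do not support that: the interval for 14/35 just reaches the independence value, four veins is an assumption, and PEFCAT, with more patients and the 75-day remap used in this trial, points the other way. PEFCAT does not settle the matter either, since its figures do not fit four veins per patient.

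A reader might also infer that per-vein durability is the number on which the next trial will be designed. The documents say only that results from this study will inform further studies; they do not single out that figure.

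None of this supplies the missing method. The SAP chose to print intervals on veins, and an interval that ignores the patient is valid only if the correlation is nil.

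**Conclusion.** The plan has no valid interval for vein-level proportions unless outcomes are independent within a patient. Five rows in Tables 4, 6 and 11 are affected. Under four veins per patient, plausible widening runs from about 0 (PEFCAT) to about 40% (IMPULSE), and 58% at a correlation of 0.5. At correlation 0.3 with 25 patients, exact 95% intervals cover about 85–92% and asymptotic ones about 76–85%. These sizes rest on the assumed number of veins and on a correlation that the documents do not give.

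The gap between 95.6% and 84.2% when every vein is isolated should not be read as the size of the error. It is the full-correlation extreme, and the patient-level limit answers a different question: whether all of a patient's veins are isolated.

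Severity is minor to moderate. The primary feasibility endpoint, chronic procedural success and all decisions are unchanged.

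**What to change.** Add to SAP 2.1.4 a rule for proportions whose unit is the vein (Tables 4, 6 and 11):
- Keep the pooled point estimate. Compute the 95% interval with the subject as cluster, by GEE or robust variance with a small-sample correction, or by a bootstrap that resamples subjects.
- At or near 100%, where those methods break down, use an exact or Agresti-Coull interval on n divided by a design effect. If every vein is isolated the data cannot estimate that design effect, so fix its value or range in advance. Alternatively, show the subject-level interval, labelled as a conservative bound.
- Apply the same rule if several extra-PV lesions per subject are pooled into one proportion.

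The minimum alternative is to drop the vein-level intervals or to footnote that they ignore correlation within patients.

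The cost is a few sentences in the SAP and a little code. No data collection or patient management changes. The downside is wider intervals, and if the correlation proves small the clustered interval will differ little from the planned one.
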